## Revision Chronology

GlaxoSmithKline Document Number	Date	Version
2015N243304_00	2015-OCT-19	Original
2015N243304_01	2016-MAR-23	Amendment No. 1

This protocol amendment was created to make the following changes:

Secondary Medical Monitor details updated to reflect changes in personnel.

IND Number added.

Section 1 and Section 3 Objective(s)/Endpoints: The wording of the primary objective was revised to reflect the pragmatic approach of the study. “To determine whether there is an improvement in asthma control when directly switched to mepolizumab, in subjects with a severe eosinophilic asthma phenotype not optimally controlled on omalizumab” changed to: “To describe in a pragmatic setting whether there is an improvement in asthma control ,from the beginning to the end of the study, when directly switched from omalizumab to mepolizumab, in subjects with a severe eosinophilic asthma phenotype not optimally controlled on omalizumab.

Section 4.6.1 Table 3: Risk assessment. “Subjects are to be monitored post-injection for one hour” was changed to “Subjects are to be monitored post-injection for one hour for the first 3 injections, then per institutional guidelines”.

Section 5.1, Inclusion criterion 6, was updated to include long-acting anticholinergic (tiotropium bromide).

Section 5.3, Required Criteria to Start Treatment. No. 2, “run-in” was added for consistency.

Section 5.5.3, Liver Chemistry Stopping Criteria “Appendix 2” was corrected to “Appendix 5” as this was a typographical error.

Section 5.5.4, QTc Stopping Criteria “change from baseline (Visit 2)”, was replaced with “change from screening (Visit 1)”. In addition, “Baseline (Visit 2)” was changed to “Screening (Visit 1)” as this was a typographical error.

Section 6.1, Investigational Product and Other Study Treatment. Ventolin Diskus for Sweden was added to reflect its use as a rescue medication in Sweden. “MDI”, was replaced by “rescue inhaler”

Section 7, Time and Event Table was updated. The “x”, in Dispense paper diary/worksheet row for The Exit Visit/Early withdrawal Visit column, was removed to correct a typographical error. In addition, in the table footnote the assay for Hepatitis C was updated.

Section 7.3.2.3.1, Pre and post bronchodilator FEV1, “long-acting anticholinergic (LAMA)” was added.

Section 7.4.7, Clinical Safety Laboratory Assessments Table 5 footnote, “Appendix 2”, was changed to “Appendix 5” as this was typographical error.

Section 7.5, Biomarker(s)/Pharmacodynamic Markers, a sentence referring to the blinding of eosinophil counts was removed.

Section 12.7 Appendix 7 Sub-section 12.7.2 last bullet point, Appendix 2 was replaced by Appendix 5 to correct a typographical error.

Typographical errors have been corrected throughout the document.

## 1. PROTOCOL SYNOPSIS FOR STUDY 204471

### Rationale

Severe asthma is associated with substantial morbidity and mortality and a large fraction of the health care cost among patients with asthma. Eosinophilic airways are associated with high risk of asthma exacerbations. Mepolizumab is an anti-interleukin-5 (IL-5) monoclonal antibody that neutralizes IL-5 and reduces eosinophil counts in both sputum and blood. Clinical trials have shown that mepolizumab reduces asthma symptoms, exacerbations, improves quality of life and is a promising intervention to manage patients with severe eosinophilic asthma.

Omalizumab an anti-immunoglobulin E (IgE) monoclonal antibody (mAb) is effective in the treatment of moderate to severe allergic asthma. However there are some patients who continue to have asthma that is not optimally controlled with omalizumab treatment.

Allergic and eosinophilic severe asthma are recognized as two distinctive phenotypes with a degree of overlap (~30%), but with differences in their associations with inflammatory biomarkers. Mepolizumab has been shown to be effective in subjects with both atopic and non-atopic asthma.

The aim of this study is to investigate whether subjects not optimally controlled on their current omalizumab treatment, who are eligible for therapy with mepolizumab can be effectively and safely switched to treatment with mepolizumab to improve asthma control. As this is a single arm study, comparisons will be made back to baseline.

The study will provide data on the efficacy, safety, immunogenicity, and tolerability of mepolizumab when switched directly from omalizumab without any wash-out. In clinical practice, mepolizumab would likely be started 2-4 weeks after the last dose of omalizumab. The learnings from this study may help guide physicians when substituting one biologic with another for the treatment of patients with severe eosinophilic asthma.

### Objective(s)/Endpoint(s)

Objectives	Endpoints
Primary	
To describe in a pragmatic setting whether there is an improvement in asthma control, from the beginning to the end of the study, when directly switched from omalizumab to mepolizumab in subjects with a severe eosinophilic asthma phenotype not optimally controlled on omalizumab	
 
Mean change from baseline in Asthma Control Questionnaire-5 (ACQ-5) score at Week 32
 

Secondary	
To determine whether there is an	
 
Mean change from baseline in St.
 

Objectives	Endpoints
improvement in Health related Quality of Life (HR-QoL) when directly switched to mepolizumab, in subjects with a severe eosinophilic asthma phenotype not optimally controlled on omalizumab	George's Respiratory Questionnaire (SGRQ) score at Week 32
To determine the frequency of asthma exacerbations, when directly switched to mepolizumab, in subjects with a severe eosinophilic asthma phenotype not optimally controlled on omalizumab.	
 
Frequency of clinically significant asthma exacerbations over 32 week treatment
 

To evaluate the pharmacodynamic effects when directly switched to mepolizumab, in subjects with a severe eosinophilic asthma phenotype not optimally controlled on omalizumab.	
 
Ratio to baseline in blood eosinophils at Week 32
 

## Overall Design

The study will be a multi-centre, open-label single arm trial. Patients with severe eosinophilic asthma who are receiving omalizumab, but are not optimally controlled will be eligible to participate and will be identified through the ACQ-5 with a screening (Visit 1) and baseline (Visit 2) score of  $\geq 1.5$  and a history of  $\geq 2$  exacerbations in the past 12 months. For those subjects receiving omalizumab for  $\geq 8$  months, at least 1 exacerbation must be while on omalizumab treatment.

Subjects meeting all the inclusion/exclusion criteria at screening Visit 1, will enter a run-in period for a minimum of one week and up to 4 weeks.

[figure not shown]
Subjects will remain on their current maintenance therapy including omalizumab throughout the run-in period. At Visit 2 subjects will discontinue their omalizumab treatment and be switched to mepolizumab 100 mg subcutaneous (SC) every 4 weeks. The treatment period is 32 weeks, including an Exit Visit/Early Withdrawal Visit, 4 weeks following the subject's last dose of mepolizumab. Except for omalizumab, subjects will remain on their current maintenance therapy throughout the treatment period.

Efficacy and safety assessments include blood tests, physical exam, ECGs, vital signs, pulmonary function tests (PFTs) and questionnaires (including ACQ-5, SGRQ, Treatment satisfaction questionnaire and patient and physician rated response to therapy).

An optional Exit interview will be conducted during the Exit Visit/Early Withdrawal Visit in a subset of participating sites and in a subset of patients who consent to participate.

The investigator is responsible for ensuring that consideration has been given to the post-study care of the patient's medical condition. At the end of the study, subjects may be prescribed appropriate alternative asthma therapy if needed and as determined by the study Investigator.

The study design is shown in the figure below

### Treatment Arms and Duration

Eligible patients will receive mepolizumab 100 mg SC every 4 weeks for 28 weeks and will be requested to participate in the study for a maximum of 38 weeks inclusive of the Exit Visit.

Approximately 155 subjects will be screened to achieve 120 treated with mepolizumab. Assuming a 15% withdrawal rate, this will result in approximately 100 evaluable subjects completing 32 weeks of mepolizumab treatment.

### Sample Size and Analysis

With a sample size of 120 treated subjects, it is estimated that this study has over 90% power to detect a statistically significant improvement from baseline. Further it is estimated that a significant improvement over the 'placebo effect' of -0.55 from baseline in ACQ score will be observed at the two-sided 5% level of significance if the observed change from baseline is at least -0.74 units.

If the true change from baseline is -0.86 units, then the study has a probability of 90% of observing a change from baseline of at least -0.74 units and therefore the study has 90% power for declaring statistical significance over the 'placebo effect'

Analysis of change from baseline in ACQ score will be performed using mixed models repeated measures (MMRM) analysis, allowing for covariates of baseline ACQ score, region, baseline maintenance oral corticosteroid (OCS) therapy, exacerbations in the year prior to the study (as an ordinal variable), visit and an interaction term for visit by baseline ACQ score.

## 2. INTRODUCTION

Eosinophilic inflammation of the airways specifically plays a central role in the pathogenesis of asthma [Kim, 2004]. Eosinophils are not present in healthy lungs, and are thought to play a major role in maintaining airway inflammation [Walsh, 2010; Wadsworth, 2011]. Studies in the severe asthma patients have shown that more than half of these patients have persistent eosinophilic (>3% sputum eosinophils) airway inflammation despite corticosteroid therapy [Wenzel, 2005; ENFUMOSA, 2003].

Of the inflammatory mediators postulated to contribute to the regulation of eosinophil trafficking and degranulation, interleukin-5 (IL-5) has been identified as the main cytokine to selectively regulate eosinophil function [Sumitas, 2011]. IL-5 specifically promotes the differentiation of eosinophils in the bone marrow and stimulates the release of eosinophils from the bone marrow into peripheral circulation [Sanderson 1992; Collins, 1995]. Binding of IL-5 to eosinophil-expressing IL-5 receptors results in enhanced adhesion of eosinophils to endothelial cells and increased eosinophil survival and activation [Lopez, 1988].

Mepolizumab is a humanized anti-interleukin 5 (anti-IL5) immunoglobulin G (IgG Kappa) monoclonal antibody (mAb) that binds to and inactivates IL-5. Mepolizumab has completed a phase III program and is under regulatory review for market authorization in a number of countries.

Recently completed studies in severe eosinophilic asthma have demonstrated mepolizumab to be effective in reducing asthma symptoms and exacerbations and in improving respiratory quality of life [Pavord, 2012; Ortega, 2014b; Bel, 2014].

### 2.1. Study Rationale

Severe asthma is associated with substantial morbidity and mortality and a large fraction of the health care cost among patients of asthma [Wenzel, 2012]. Eosinophilic airways, and high eosinophil count blood is associated with frequent asthma exacerbations (Tran, 2014). Completed clinical trials have shown that mepolizumab, neutralizes IL-5 and reduces eosinophil counts in both sputum and blood (Pavord, 2012) and is a promising intervention to manage patients with severe eosinophilic asthma.

Omalizumab an anti-immunoglobulin E (IgE) monoclonal antibody (mAb) is effective in the treatment of moderate to severe allergic asthma. [European medicines Agency EMEA, 2015] summary of product characteristics (SmPC); Xolair US prescribing information, 2014]. However there are some patients who continue to have asthma that is not optimally controlled with omalizumab treatment.

The key principle of treatment management is to achieve asthma control with a goal of improving symptoms and reducing future risk [Chung, 2014]. Due to the heterogeneous nature of asthma, no single clinical parameter completely reflects asthma control. Multiple measures are important as each may assess different domains of disease, including health related quality of life.

Allergic and eosinophilic severe asthma are recognized as two distinctive phenotypes with a degree of overlap (~30 %) but with also differences in their associations with inflammatory biomarkers [Chung, 2014]. Mepolizumab has been shown to be effective in subjects with both atopic and non-atopic asthma [Ortega, 2014a]. With the availability of mAbs with different mechanisms of action, the opportunity for personalized and specifically targeted treatment becomes possible.

The aim of the present study is to investigate whether subjects not optimally controlled on their current omalizumab treatment, who are eligible for therapy with mepolizumab can be effectively and safely switched to treatment with mepolizumab to improve asthma control. As this is a single arm study, comparisons will be made back to baseline.

The study will provide data on the efficacy, safety, immunogenicity, and tolerability of mepolizumab when switched directly from omalizumab without a wash-out period of approximately 4.5 months. In clinical practice, mepolizumab would likely be started 2-4 weeks after the last dose of omalizumab. The learnings from this study may help physicians when substituting one biologic with another for the treatment of patients with severe eosinophilic asthma.

## 2.2. Brief Background

Severe asthma represents approximately 5-10% of the asthma population and is associated with a greater frequency of asthma exacerbations, and a greater symptom burden [Chung, 2014; Moore, 2007]. Asthma is a heterogeneous condition characterized by airflow obstruction, bronchial hyper responsiveness and underlying inflammation. Eosinophils are major effector cells involved in the initiation and propagation of diverse inflammatory responses and are considered a central mediator of asthma pathology [Catley, 2011]. An increase in eosinophils is associated with cough, airway remodelling, worse lung function and asthma exacerbations which are, in-turn, associated with a more rapid decline in forced expiratory volume in 1 second (FEV1) [Desai, 2012; O'Byrne, 2011].

Mepolizumab is a humanised monoclonal antibody that binds to and inactivate interleukin-5, a cytokine that recruits eosinophils from the bone marrow and promotes the persistence and activation of these cells [Sumitas, 2011; Pavord, 2012].

Completed phase III studies with mepolizumab have demonstrated the efficacy of mepolizumab and support the use of mepolizumab 100 mg subcutaneous (SC) every 4 weeks as an add-on therapy for the treatment of severe eosinophilic asthma. Compared with placebo, mepolizumab has been shown to:

- Reduce the rate of clinically significant exacerbations by approximately 50%. [Pavord, 2012, Ortega, 2014b].
- Reduce the rate of exacerbations requiring hospitalisations and/or Emergency Department (ED) visits, with reductions ranging from 32% to 61% [Pavord, 2012, Ortega, 2014b].

- Produce statistically significant and/or clinically relevant improvements in lung function based on FEV1, improvement in Asthma Control Questionnaire (ACQ-5), St. George's Respiratory Questionnaire (SGRQ) and clinician and subject-rated overall response to therapy [Ortega, 2014b, Bel, 2014]
- Consistently reduce blood eosinophil levels detected at Week 4 and sustained for the duration of treatment [Pavord, 2012, Ortega, 2014b, Bel, 2014].

Additional details of the pharmacology, efficacy and safety can be found in the Investigator Brochure (IB).

### 3. OBJECTIVE(S) AND ENDPOINT(S)

**Table 1** Study Objectives and Endpoints

Objectives	Endpoints
Primary	
To describe in a pragmatic setting whether there is an improvement in asthma control, from the beginning to the end of the study, when directly switched from omalizumab to mepolizumab in subjects with a severe eosinophilic asthma phenotype not optimally controlled on omalizumab	
 
• Mean change from baseline in ACQ-5 score at Week 32
 

Secondary	
To determine whether there is an improvement in Health related Quality of Life (HR-QoL) when directly switched to mepolizumab, in subjects with a severe eosinophilic asthma phenotype not optimally controlled on omalizumab	
 
• Mean change from baseline in SGRQ score at Week 32
 

To determine the frequency of asthma exacerbations, when directly switched to mepolizumab, in subjects with a severe eosinophilic asthma phenotype not optimally controlled on omalizumab.	
 
• Frequency of clinically significant asthma exacerbations over 32 week treatment
 

To evaluate the pharmacodynamic effects when directly switched to mepolizumab, in subjects with a severe eosinophilic asthma phenotype not optimally controlled on omalizumab.	
 
• Ratio to baseline in blood eosinophils at Week 32
 

Others	
To determine the response to asthma clinical parameters when directly switched to mepolizumab in subjects	
 
• Percentage of subjects achieving a 0.5-point or greater reduction from
 

Objectives	Endpoints
with a severe eosinophilic asthma phenotype not optimally controlled on omalizumab.	
baseline in ACQ-5 score at Week 32
 
 
Percentage of subjects achieving a 4-point or greater reduction from baseline in SGRQ score at Week 32
 
Mean change from baseline in pre- and post bronchodilator FEV1 at Week 32
 
Frequency of exacerbations requiring ED visit/hospitalization during the treatment period
 
Subject/Clinician rated response to therapy
 
Mean change from baseline in treatment satisfaction questionnaire
 

Exploratory	

To determine the effect on inflammatory biomarkers, when directly switched to mepolizumab, in subjects with a severe eosinophilic asthma phenotype not optimally controlled on omalizumab
 
To characterize patient treatment benefit of mepolizumab
	
 
Change from baseline in some inflammatory biomarkers expression at week 32.
 
Subject Exit Interviews
 

Safety	
To determine the safety, immunogenicity and tolerability of mepolizumab when directly switched to mepolizumab, in subjects with a severe eosinophilic asthma phenotype not optimally controlled on omalizumab.	
 
Incidence and frequency of Adverse/Serious Adverse Events (including systemic and injection site reactions)
 
Clinically significant change in electrocardiogram (ECGs)
 
Clinically significant change in vital signs
 
Incidence of immunogenicity
 

## 4. STUDY DESIGN

### 4.1. Overall Design

The study will be a multi-centre, open-label single arm trial. Patients with severe eosinophilic asthma who are receiving omalizumab, but are not optimally controlled will be eligible to participate and will be identified through the ACQ-5 with a screening (Visit 1) and baseline (Visit 2) score of  $\geq 1.5$  and a history of  $\geq 2$  exacerbations in the past 12 months. For those subjects receiving omalizumab for  $\geq 8$  months, at least 1 exacerbation must be while on omalizumab treatment.

Subjects meeting all the inclusion/exclusion criteria at screening Visit 1, will enter a run-in period for a minimum of one week and up to 4 weeks to assess subjects' eligibility and compliance with study-related procedures.

[figure not shown]
Subjects will remain on their current maintenance therapy throughout the run-in period, including omalizumab. At Visit 2 subjects will discontinue omalizumab treatment and be switched to mepolizumab 100 mg SC every 4 weeks. Except for omalizumab, subjects will remain on their current maintenance therapy throughout the open-label treatment period.

Every subject, including those who withdraw early from the study, will be asked to return for an Exit Visit approximately 4 weeks after their last dose of study treatment.

An Exit interview will be conducted during the Exit Visit or early withdrawal Visit in a subset of participating sites and in a subset of patient who consent to participate.

The investigator is responsible for ensuring that consideration has been given to the post-study care of the patient's medical condition. At the end of the study, subjects may be prescribed appropriate alternative asthma therapy if needed and as determined by the study Investigator.

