**Figure 1 Study Design**

## 4.2. Treatment Arms and Duration

Eligible patients will receive mepolizumab 100 mg SC every 4 weeks for 28 weeks and will be requested to participate in the study for a maximum of 38 weeks (Visit 0 to the Exit Visit (Visit 10), inclusive as described in [Table 2](#)).

**Table 2** Study phases

Phase	Phase Title	Duration	Description
1	Pre-screening	0 to 2 weeks	At the Pre-screening Visit, details about the study and procedures will be explained through the informed consent process. The Pre-screening Visit (Visit 0) can occur on the same day as the Screening Visit (Visit 1) but must be completed prior to initiating any Visit 1 procedures.
2	Screening / Run-in	1 to 4 weeks	Subjects who meet all the eligibility criteria at Screening, will enter the run-in period for a minimum of 1 week and a maximum of 4 weeks in order to continue to assess the subject's eligibility for the study. Subjects who experience an asthma exacerbation during the run-in period should receive treatment for their exacerbation and remain in the run-in period until the investigator considers that the subject has returned to their baseline asthma status for at least one week. Those subjects that are not eligible to continue in the study at the end of the 4 week run-in period will be deemed run-in failures (see Section 5.4 ).
3	Treatment	32 weeks	At Visit 2 (Week 0) those subjects who successfully complete the run-in period as well as meet the other pre-defined eligibility and continuation to treatment criteria (see Section 5.3 ) will receive mepolizumab 100 mg SC every 4 weeks for a total of 8 doses.  The treatment period will conclude with subjects completing Exit Visit (Visit 10) assessments approximately 4 weeks after the subject was administered their last dose of study treatment at Visit 9.

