## 5.5. Withdrawal/Stopping Criteria

### 5.5.1. Withdrawal from Study Treatment

Subjects may be withdrawn from study treatment at any time by the Investigator if it is considered to be detrimental for them to continue in the study. Reasons for withdrawal from study treatment can include: an adverse event (including abnormal liver function test or abnormal laboratory results), clinically significant abnormality identified on ECG, lost to follow-up, protocol violation, lack of efficacy, sponsor terminated study, non-compliance, continued in error, pregnancy, or for any other reason.

Subjects who have permanently withdrawn mepolizumab study treatment are not required to withdraw from the study. Every effort should be made to complete all remaining protocol specified visits even if they have discontinued mepolizumab treatment provided there are no safety concerns with doing so.

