## 5.6. Subject and Study Completion

A subject will be considered to have completed study treatment if he/she receives study treatment at Visit 9 (Week 28) and completes the Exit Visit (Week 32). A subject will be considered to have completed the study if they continue to participate in the study until the Exit Visit assessments have been completed (regardless of whether the subject completed the study treatment schedule).

The end of the study is defined as the last subject's last visit.

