## 7.1. Time and Events Table

Procedures	Pre-screen 	Screen Run-in	Treatment (visit window is $\pm 7$ days)									Exit Visit/ Early withdrawal Visit 
			0	1	2	3	4	5	6	7	8	
Visit	0	1										10
Week	-6 to -4	-4 to -1	0	4	8	12	16	20	24	28		4 weeks post last dose $\pm 7$ days
Informed Consent 	x											
Subject Demography	x											
Medical History		x										
Asthma History (including triggers)	x	x										
Therapy History 		x										
Smoking History		x										
Cardiovascular History/Risk Factors		x										
Inclusion/Exclusion Criteria		x										
Continuation to treatment Criteria			x									
Efficacy Assessments 												
ACQ-5		x	x	x	x	x	x	x	x	x	x	x
Exacerbation review	x	x	x	x	x	x	x	x	x	x	x	x
Spirometry including pre- and post bronchodilator FEV 1 , FVC 		x	x			x			x			x
Health Outcome Assessments 												
SGRQ			x			x			x		x	x

Procedures	Pre-screen 	Screen Run-in	Treatment (visit window is $\pm 7$ days)									Exit Visit/ Early withdrawal Visit 
			0	1	2	3	4	5	6	7	8	
Visit	0	1	2	3	4	5	6	7	8	9	10	
Week	-6 to -4	-4 to -1	0	4	8	12	16	20	24	28	4 weeks post last dose $\pm 7$ days	
Clinician & Subject rated response to therapy					x		x		x			x
Treatment Satisfaction with Medication Questionnaire (TSQM-9)		x										x
Exit Interview 												x
Safety Assessments												
Concomitant Medication	x	x	x	x	x	x	x	x	x	x	x	
Physical Examination, including nasal exam		x										x
Vital Signs		x	x	x	x	x	x	x	x	x	x	
12 lead ECG		x				x						x
Adverse Events		x	x	x	x	x	x	x	x	x	x	
Serious Adverse Events	x	x	x	x	x	x	x	x	x	x	x	
Laboratory Assessments												
Haematology with differential		x	x	x	x	x	x	x	x	x	x	
Clinical Chemistry (incl. LFT)		x	x	x	x	x			x			x
Parasitic Screening 		x										
Pharmacogenetic sample 							x					
Pregnancy test 		U	U	U	U	U	U	U	U	U	U	U
HBsAg and hepatitis C antibody 		x										
Immunogenicity sample			x			x				x		x
Biomarker sample		x	x		x							x

Procedures	Pre-screen 	Screen Run-in	Treatment (visit window is $\pm 7$ days)									Exit Visit/ Early withdrawal Visit 
Visit	0	1	2	3	4	5	6	7	8	9	10	
Week	-6 to -4	-4 to -1	0	4	8	12	16	20	24	28	4 weeks post last dose $\pm 7$ days	
Investigational product (Mepolizumab) and rescue medication												

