Administer mepolizumab. Contact RAMOS NG to register dispensing visit.			X	X	X	X	X	X	X	X		
Albuterol/salbutamol dispensed (as needed)		X	X	X	X	X	X	X	X	X		
Collect dispensed albuterol/salbutamol			X	X	X	X	X	X	X	X	X	
eCRF/ paper diary/worksheet												
Complete eCRF	X	X	X	X	X	X	X	X	X	X	X	
Dispense paper diary/worksheet	X	X	X	X	X	X	X	X	X	X		
Collect/review paper diary/worksheet		X	X	X	X	X	X	X	X	X	X	
1. Pre-screen Visit 0 must be completed prior to Visit 1 (Screening). It can be completed on the same day as Visit 1 or at up to 2 weeks prior to Visit 1. 2. Subjects will be assigned a subject number at the time ICF signed. The ICF must be signed before any study procedures including medication wash out period(s). 3. Exit Visit may be completed 3 to 5 weeks post last dose. 4. Therapy history to include a detailed review of prior biologics received for treatment of asthma, including omalizumab dose and regimen and prior investigational therapies e.g anti-IL5 or anti-IL13 preparations. 5. All study efficacy, safety and all patient reported questionnaires must be completed prior any study procedure. 6. Spirometry to include pre- and post bronchodilator FEV1 from V2. 7. Exit interview will be conducted only in a subset of sites and in a subset of subjects who choose to participate in the Exit interview. Subjects must be consented prior to interview 8. Parasitic screening is only required in countries with high-risk or for subjects who have visited high-risk countries in the past 6 months. Sites should use local laboratories. 9. Pharmacogenetic sample may be drawn at Visit 2 or any visit after. 10. Pregnancy test, U= urine 11. Hepatitis B Surface Antigen and Hepatitis C antibody. (if hepatitis C antibody is positive, hepatitis C will be confirmed by PCR).												

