#### **9.4.1. Primary Analyses**

Analysis of change from baseline in ACQ score will be performed using a mixed models repeated measures (MMRM) analysis, allowing for covariates of baseline ACQ score, region, baseline maintenance OCS therapy, exacerbations in the year prior to the study (as an ordinal variable), visit and an interaction term for visit by baseline ACQ score. The primary comparison will be Week 32 vs. Baseline and all data collected up to and including Week 32 from patients, including those who have discontinued study treatment, will be included in the analysis.

The primary population for analysis will be the ITT population. A supporting analysis of the PP population will also be performed.

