10.3. Appendix 3: Assessment Windows & Visit Slotting

10.3.1. Assessment Windows

Clinic visits are scheduled to take place as specified in [Appendix 2: Time & Events](#). Measurements outside visit windows will not be excluded from analyses. For all clinic visits, nominal visit days and times will be used for reporting, such that if a subject recorded values that were outside of the ± 7 day window for a visit they will still be reported under that visit.

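### The Exit Visit is timed only from the last dose, which conflicts with follow-up to Week 32 and leaves subjects who stop mepolizumab early but stay in the study without an assured Week 32 ACQ-5

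*Protocol*

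**What the plan says.** **Timing of Visit 10.** Protocol 4.1 states that every subject, early withdrawals included, "will be asked to return for an Exit Visit approximately 4 weeks after their last dose of study treatment". The Visit 10 column of the Time and Events Table (Protocol 7.1, repeated in SAP 10.2.1) is a combined Exit and Early Withdrawal column. It is timed at 4 weeks after the last dose, plus or minus 7 days, with no study week. Footnote 3 adds: "Exit Visit may be completed 3 to 5 weeks post last dose".

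**Dosing.** Under Protocol 4.2, subjects "will receive mepolizumab 100 mg SC every 4 weeks for a total of 8 doses", at Weeks 0 to 28. A subject given all 8 doses therefore reaches Visit 10 at Week 32.

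**Subjects who stop drug.** Protocol 5.5.1 does not require them to leave the study: "Every effort should be made to complete all remaining protocol specified visits even if they have discontinued mepolizumab treatment". Protocol 5.6 counts subjects as having completed the study "if they continue to participate in the study until the Exit Visit assessments have been completed", whether or not they completed treatment.

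**Analysis.** Protocol 9.4.1, followed by SAP 7.1.2, says that "all data collected up to and including Week 32 from patients, including those who have discontinued study treatment, will be included in the analysis".

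**Labelling.** SAP 10.3.1 reports by nominal visit. If values were recorded "outside of the ± 7 day window for a visit they will still be reported under that visit". SAP 10.3.2 moves data from Early Withdrawal or Treatment Discontinuation Visits to the nearest visit at which the endpoint was due, but its operative condition is that the subject withdraws from the study.

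**The concern.** The primary endpoint is the change in ACQ-5 at Week 32, and Visit 10 is the only visit in the schedule that can supply it. The timing rule for that visit looks only at the last dose. The follow-up and analysis rules look to Week 32 whether or not dosing continued. For a subject who stops early and stays, the two sets of rules point to different dates, and no passage gives Visit 10 a study-week anchor for that subject.

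A site that follows the last-dose rule collects no Week 32 value. The off-drug data that Protocol 9.4.1 asks for are then missing, and Protocol 9.2.1 handles missing data under missing at random. If that early visit is entered as Visit 10, a score taken 3 to 5 weeks after the last dose may instead be analysed as Week 32. There is no control arm in which the same error would also occur.

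The last-dose reading is plausible for a site. Protocol 7.3.2.4 also ends exacerbation collection about 4 weeks after the last dose for subjects who stop treatment early, although SAP 8.1.2 wants exacerbation data up to Week 32 from the same subjects.

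**Working it through.** **1. The plan's own figures.** Inputs from Protocol 9.2.1: 120 treated, 15% missing at Week 32, residual SD 0.96, reference change -0.55, true change -0.86, two-sided 5%.

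- n = 120 x 0.85 = 102
- SE = 0.96/√102 = 0.0951
- Critical change = -0.55 - 1.96 x 0.0951 = -0.736, which rounds to the stated -0.74
- Power = Φ((0.86 - 0.55)/0.0951 - 1.96) = 90.3% (89.8% with the t distribution), against the stated 90%

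The stated figures are reproduced at n = 102. With n = 120 the power would be 94%, so the planned figures already allow for 15% missing Week 32 values.

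**2. Where Visit 10 falls under the last-dose rule.** Last dose week = 4 x (doses - 1). Visit 10 = last dose week + 4, with a window of + 3 to + 5.

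| Doses received | Last dose (week) | Visit 10 (week) | Window (weeks) | Weeks before Week 32 |
|---|---|---|---|---|
| 1 | 0 | 4 | 3-5 | 28 |
| 2 | 4 | 8 | 7-9 | 24 |
| 3 | 8 | 12 | 11-13 | 20 |
| 4 | 12 | 16 | 15-17 | 16 |
| 5 | 16 | 20 | 19-21 | 12 |
| 6 | 20 | 24 | 23-25 | 8 |
| 7 | 24 | 28 | 27-29 | 4 |
| 8 | 28 | 32 | 31-33 | 0 |

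For 1 to 7 doses the visit is 4 to 28 weeks early at nominal timing. With the window the range is 32 - 29 = 3 to 32 - 3 = 29 weeks.

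**3. Can both rules be met?** Visit 10 can lie 3 to 5 weeks after the last dose and also in Weeks 31 to 33 only if the last dose is between Week 31 - 5 = 26 and Week 33 - 3 = 30. Of the 8 dosing visits, only Week 28 qualifies. A Week 24 dose given a week late, followed by the latest permitted visit, reaches only 25 + 5 = Week 30.

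**4. Visit order.** Visit 9 is at Week 28. A subject whose last dose was at Week 8 and who attends every remaining visit is 28 - 8 = 20 weeks past the last dose by Visit 9. A Visit 10 held after that breaks the 3-to-5-week rule. A Visit 10 held at Weeks 11 to 13 comes before Visits 6 to 9, and Protocol 5.6 would then allow that subject to be counted as a study completer.

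**5. Size if values are mislabelled (illustration only).** If a share f of the Week 32 values is mislabelled and each differs by d from the true Week 32 value, the mean shifts by f x d. The documents give neither input. For f = 1% to 15% and d = 0.1 to 0.5:

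- smallest shift: 0.01 x 0.1 = 0.001
- largest shift: 0.15 x 0.5 = 0.075

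At a true -0.86, the largest shift would move the chance of passing the -0.55 comparison to Φ((0.31 - 0.075)/0.0951 - 1.96) = 70% if it is toward zero, or Φ((0.31 + 0.075)/0.0951 - 1.96) = 98% if away from zero. The comparison with baseline is not sensitive at this scale: its power already exceeds 99.9% at a true change of -0.55.

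**The case against.** The strongest reply is that other passages settle the matter. Protocol 5.5.1 asks subjects who stop drug to attend all remaining visits, and Visit 10 is the last in the sequence. Protocol 4.4, 5.6 and 7.3.2.4 all treat the Exit Visit as Week 32. On labelling, SAP 10.3.2 names Treatment Discontinuation Visits, and its worked example moves a Week 16 FEV1 to Week 12, not to Week 32. ACQ-5 is collected at every visit, so an adjacent slot always exists. SAP 10.4.2 separates Visit 10 for completers from an Early Withdrawal/Treatment Discontinuation visit for others. SAP 10.5.3 says that the impact of major timing deviations will be assessed as appropriate.

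Much of this stands, and it rules out several stronger readings that a reader might infer:

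- **That every such subject has Visit 10 too early.** The documents conflict and do not settle the date. The visit can fall early.
- **That early values will routinely be labelled Week 32.** SAP 10.3.2 re-slots the visits of subjects who withdraw from the study. Mislabelling needs a subject who stops drug, stays, and has the visit entered as Visit 10.
- **That the effect will be overstated.** Lack of efficacy and adverse events are among the listed reasons for stopping, so an early score could be poor. The direction is unknown.
- **That up to 15% of subjects are affected, or that precision drops from 120 to 102.** The 15% is study withdrawal with missing Week 32 data, not stopping drug while staying, and that loss is already in the planned figures.

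The reply does not remove the conflict. None of these passages gives Visit 10 a study-week anchor for someone who stops early. The Treatment Discontinuation Visit named in the SAP is not in the schedule, and the condition in SAP 10.3.2 does not clearly cover subjects who stay. The undertaking in SAP 10.5.3 contains no rule.

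**Conclusion.** The concern holds as a conflict between rules for the primary endpoint visit. The last-dose timing in Protocol 4.1, the Time and Events Table and SAP 10.2.1 cannot be followed together with Protocol 5.5.1 and the Week 32 analysis in Protocol 9.4.1 and SAP 7.1.2 for any subject who stops after 1 to 7 doses and stays. Protocol 5.6 would let the early visit count as study completion. The timing result rests on the documents' own schedule and needs no outside assumption.

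The effect on the estimate cannot be sized from the documents. The shift of 0.001 to 0.075 rests on assumed shares and differences and carries no sign. At that scale it could matter for the comparison with the historical placebo effect, which SAP 7.1.2 lists as supportive, but not for the test against baseline. The planned n = 102, the -0.74 threshold and the 90% power stand.

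**What to change.** Reconcile the passages as follows. The changes concern assessment timing and labels, not dosing or stopping rules.

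- **Protocol 4.1, Time and Events Table and footnote 3, SAP 10.2.1:** schedule the Week 32 assessment (plus or minus 7 days) from Visit 2 for every subject still in the study, on or off drug. Give the post-last-dose visit its own label, Early Withdrawal/Treatment Discontinuation.
- **Protocol 5.6 (and SAP 10.7.1, which repeats it):** tie study completion to the Week 32 visit.
- **SAP 10.3:** state that a visit timed from an early last dose is slotted by study day and not reported as Week 32, and that this covers subjects who stop drug but stay.

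The cost is wording in both documents and one visit label in the eCRF. Nothing changes for subjects who complete dosing. The downside is one later clinic visit for the subjects who stop early and stay, who are already asked to attend the remaining visits.
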